Exclusion Criteria	
A subject must NOT MEET ANY of the following exclusion criteria:
 
 1. Had previous lumbar spinal surgery (e.g., lumbar fusion, discectomy, laminectomy, laminotomy) 2. Has a medical, anatomical, and/or psychosocial condition that is contraindicated for commercially available Intellis™ SCS systems as determined by the Investigator 3. Has a diagnosed back condition with inflammatory causes of back pain (e.g., onset of severe pain with activity), serious spinal pathology and/or neurological disorders, as determined by the Investigator 4. Be concurrently participating in another clinical study 5. Has an existing active implanted device such as a pacemaker, another SCS unit, peripheral nerve stimulator, and/or drug delivery pump, etc. 6. Has a pain in other area(s) and/or medical condition requiring the regular use of significant pain medications that could interfere with accurate pain reporting, and/or confound evaluation of study endpoints, as determined by the Investigator 7. Has mechanical spine instability as determined by the Investigator 8. Has undergone, within 30 days prior to enrollment, an interventional procedure and/or surgery to treat back and/or leg pain, which is providing significant pain relief 9. Has unresolved major issues of secondary gain (e.g., social, financial, legal), as determined by the investigator

	
10. Be involved in an injury claim under current litigation or has a pending or approved worker's compensation claim
 
11. Be pregnant (determined by urine testing unless female subject is surgically sterile or post-menopausal. If female, sexually active, and childbearing age, subject must be willing to use a reliable form of birth control.)

Primary Endpoint	The primary efficacy endpoint is the percentage of randomized subjects who respond (a decrease in back pain VAS by at least 50% compared to baseline) to SCS therapy at 3 months (non-inferiority analysis). Subjects who do not have a successful Trial Phase are considered failures (non-responders) toward the primary endpoint.

Table of Contents

CLINICAL INVESTIGATIONAL PLAN	1
Study Synopsis.....	2
A. Purpose.....	7
A.1. Study Device	7
A.2. Purpose of the Investigation.....	7
A.3. Study Size	7
A.4. Duration of the Investigation	8
B. Protocol	8
B.1. Rationale for Study.....	8
B.2. Study Objectives	10
B.3. Selection of Study Population	10
B.3.1. Study Population	10
B.3.2. Inclusion Criteria.....	10

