8. Be willing to not increase pain medications from baseline through the 3-Month Visit
9. Be willing and able to comply with study-related requirements, procedures, and visits

B.3.3. Exclusion Criteria

In order to participate in the study, a subject must *NOT* MEET ANY of the following exclusion criteria:

1. Had a previous spinal surgery (e.g., lumbar fusion, discectomy, laminectomy, laminotomy)
2. Has a medical, anatomical, and/or psychosocial condition that is contraindicated for commercially available Intellis™ SCS systems as determined by the Investigator
3. Has a diagnosed back condition with inflammatory causes of back pain (e.g., onset of severe pain with activity), serious spinal pathology and/or neurological disorders as determined by the Investigator
4. Be concurrently participating in another clinical study
5. Has an existing active implanted device such as a pacemaker, another SCS unit, peripheral nerve stimulator, and/or drug delivery pump, etc.
6. Has pain in other area(s) and/or medical condition requiring the regular use of significant pain medications that could interfere with accurate pain reporting, study procedures, and/or confound evaluation of study endpoints, as determined by the Investigator
7. Has mechanical spine instability as determined by the Investigator
8. Has undergone, within 30 days prior to enrollment, an interventional procedure and/or surgery to treat back and/or leg pain, which is providing significant pain relief
9. Has unresolved major issues of secondary gain (e.g., social, financial, legal), as determined by the investigator
10. Be involved in an injury claim under current litigation or has a pending or approved worker's compensation claim
11. Be pregnant (determined by urine testing unless female subject is surgically sterile or post-menopausal. If female, sexually active, and childbearing age, subject must be willing to use a reliable form of birth control.)

B.4. Treatment Groups

Subjects meeting the study entrance criteria will be randomized to one of two study treatment groups in a 1:1 ratio:

- Control Treatment Group: Conventional SCS programming approach
 - Stimulation parameters in the 40-250 Hz frequency range will be trialed according to standard practice as described in the Intellis™ labeling/manuals
 - If frequency parameter above 250 Hz is used during the study, the subject will be counted as failure towards Conventional SCS programming approach but will continue to permanent implant.

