B.7. Study Endpoints

B.7.1. Definition of Analysis Populations

- Modified Intent to Treat (mITT): All successfully randomized subjects who complete the Trial Phase.
- Intent-to-Treat (ITT): All successfully randomized subjects who met all the enrollment criteria.
- Per-Protocol (PP): All subjects who received a permanent device implant and contributed their data to the 3-month endpoint without any major protocol deviations or adverse events (that would render their data unevaluable).

The primary analysis of the primary and secondary endpoints will be performed on the mITT population. Supportive analyses will be performed for the Intent-to-Treat and Per-Protocol population.

For analyses incorporating crossover data (i.e. data gathered in the post 6-month periods), analyses will be based on the mITT population with treatment group defined by the treatment status at the corresponding time point to capture the impact of crossover. Additional sensitivity analyses censoring data post-crossover will be performed to examine the impact of crossover.

B.7.2. Effectiveness Assessment Definitions

- Primary Effectiveness Assessment: For subjects who have a successful Trial Phase and receive a permanent implant, the Primary Efficacy Assessment occurs at the follow up visit 3 months after Device Activation. For subjects who do not have a successful Trial Phase (based on subject's pain score) or subjects who do not want a permanent device implant due to insufficient pain relief (based on subject's discontinuation reason), the Primary Efficacy Assessment occurs at the end of the Trial Phase.

B.7.3. Primary Endpoint

Pain rating on the 10 cm Visual Analog Scale is considered the primary outcome measure. VAS is the most widely used outcome measure in assessing pain due to its documented reliability and validity, ease in administration, and minimal training requirements for the administrator.

- ***Individual Responder:*** A decrease in back pain VAS by at least 50% at 3 months after Permanent Device Activation as compared with Baseline. All subjects must be using the assigned programming parameters. If a subject is switched to a programming parameter that is not considered to be DTM-SCS nor Conventional SCS programming the subject will be counted as a non-responder for the following follow-up visit if one of the two following conditions exist:

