 - If a subject is switched to a programming parameter that is not considered to be DTM-SCS nor Conventional SCS programming for a period over two weeks
 - If a subject is switched to a programming parameter that is not considered to be DTM-SCS nor Conventional SCS programming for any length of time within the 2 weeks prior to a follow-up visit.

Overall Study Success: The percentage of Individual Responders in the test group is shown to be statistically non-inferior to the percentage in the control group.

B.7.4. Secondary Endpoints

The following secondary endpoints will be evaluated:

- Comparison of the percentage of Individual Responders between the test and control groups in a statistical test of superiority over time (i.e. based on repeated measures analysis). In addition, data will be summarized at the individual time points at 3 months, 6 months, 9 months, and 12 months. This will be performed based on all observed data with treatment defined as a time dependent covariate, and additionally based on censoring data post-crossover.

- Comparison of change from Baseline in back pain score (VAS) between test and control in statistical tests of non-inferiority and superiority. This is calculated as: Change from Baseline in Back Pain VAS = Follow-up Visit Pain VAS – Baseline Pain VAS. A negative result reflects a decrease in the Pain VAS, while a positive result reflects an increase in Pain VAS. All subjects must be using the assigned programming parameters. If a subject is switched to a programming parameter that is not considered to be DTM-SCS nor Conventional SCS programming, that subject's Baseline Back Pain VAS will be used instead of Follow-up Visit VAS after the programming change has occurred for the following follow-up visit if one of the two following conditions exist:
 - If a subject is switched to a programming parameter that is not considered to be DTM-SCS nor Conventional SCS programming for a period over two weeks
 - If a subject is switched to a programming parameter that is not considered to be DTM-SCS nor Conventional SCS programming for any length of time within the 2 weeks prior to a follow-up visit.

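### If *failure* in B.4 means primary non-responder, B.4 and B.7.3 score brief Control use above 250 Hz differently, and B.4 can only lower the Control responder count or leave it unchanged

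*Combined protocol and SAP*

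**What the plan says.** B.4 (Treatment Groups) limits Control to 40-250 Hz. It then says: "If frequency parameter above 250 Hz is used during the study, the subject will be counted as failure towards Conventional SCS programming approach", and adds that the subject still goes on to implant. It states no minimum duration and no time window, and the Test-arm paragraph has no such rule.

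B.7.3 (Primary Endpoint) defines an Individual Responder by a fall of at least 50% in back pain VAS at 3 months. It adds: "All subjects must be using the assigned programming parameters". It then deals with a switch to programming that is "not considered to be DTM-SCS nor Conventional SCS programming the subject will be counted as a non-responder for the following follow-up visit", provided that one of two conditions holds. Either the programming lasted more than two weeks, or it was used "for any length of time within the 2 weeks prior to a follow-up visit". These conditions apply to both arms. B.7.4 uses the same two conditions for VAS change, with this consequence: "Baseline Back Pain VAS will be used instead of Follow-up Visit VAS after the programming change has occurred".

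Two other places bear on the meaning of *failure*. The synopsis says "Subjects who do not have a successful Trial Phase are considered failures (non-responders) toward the primary endpoint". B.7.2 fixes the time of assessment: "For subjects who have a successful Trial Phase and receive a permanent implant, the Primary Efficacy Assessment occurs at the follow up visit" at 3 months. B.4 and B.7.3 do not refer to each other.

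**The concern.** The count of Control responders enters the only study-success test (B.8.2, B.9.2.1) and the 3-month superiority test that follows it (B.9.2.2). If the B.4 rule is a primary-endpoint rule, the analyst has two stated rules for the same event. One is unconditional and applies to Control alone. The other has a time threshold and applies to both arms. The choice between them would be made in an open-label trial, and B.4 can shift the comparison in one direction only. The synopsis makes that reading plausible, and the plan states no other consequence for a B.4 failure.

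**Working it through.** **1. The plan's own figure.** Inputs from B.5.5.1: responder rates 70% (Test) and 50% (Control), margin 10 points, one-sided alpha 0.05, 50 per arm. Exact enumeration of the Farrington-Manning test gives 92.7% power, which agrees with the stated 90% or greater. The sample size is not in question.

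**2. The two rules side by side.** A single-rate 300 Hz program is outside Conventional (40-250 Hz). It is also not DTM-SCS, because B.4 requires a DTM-SCS group to contain two or more programs with different rates. Take subjects with at least 50% relief at month 3 while on assigned programming:

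| Case | B.4, if failure = non-responder | B.7.3 conditions |
|---|---|---|
| Control, 300 Hz for 3 days of the Trial Phase | failure | neither met |
| Control, 300 Hz for one week early in follow-up, ending more than two weeks before a visit | failure | neither met |
| Test, same one-week use | no rule | neither met |
| Control, crosses over after month 6 to a DTM-SCS group with a rate above 250 Hz | failure, read literally | month-3 response unaffected |

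In the first row, the Trial Phase lasts at most 10 days, so use confined to it cannot exceed two weeks. The 1-month visit (±15 days) falls about 15 days or more after activation, so such use cannot lie within the two weeks before a visit. In the second row, B.7.4 would still use the subject's observed VAS, so the same subject could be a B.4 failure and still contribute a good VAS change.

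**3. Direction.** A recoded subject stays in the denominator and can only move from responder to non-responder. At 50 per arm each such move lowers the Control rate by 1/50 = 2 points. If the subject had not responded anyway, nothing changes.

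**4. Count effect at 50 per arm** (critical value 1.645).

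Non-inferiority: z = (p_T − p_C + 0.10)/SE, with SE from the Farrington-Manning restricted estimates.
- 25 Control responders: 29 Test responders give 0.18/0.0992 = 1.81 (pass); 28 give 0.16/0.0993 = 1.61 (fail).
- 24 Control responders: 28 give 0.18/0.0994 = 1.81 (pass); 27 give 0.16/0.0995 = 1.61 (fail).

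Superiority: B.9.2.2 names only a test of the difference in proportions, so a pooled z is assumed, z = (p_T − p_C)/√(p(1−p)·2/50).
- 25 Control responders: 34 give 0.18/√(0.59×0.41×0.04) = 1.83 (pass); 33 give 0.16/√(0.58×0.42×0.04) = 1.62 (fail).
- 24 Control responders: 33 give 0.18/√(0.57×0.43×0.04) = 1.82 (pass); 32 give 1.61 (fail).

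Each recoded Control responder therefore lowers the Test count needed by one in both tests. With two recoded, the counts are 27 and 32.

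**5. Hypothetical shares.** The documents give no frequency of use above 250 Hz. Suppose 2%, 5% or 10% of Control responders are recoded, so that the Control rate becomes 0.50(1−f) = 49%, 47.5% or 45%. With Test at 40%, the chance of declaring non-inferiority moves from 4.7% to 5.8%, 7.9% or 12.6%. At the planning rates, non-inferiority power moves from 92.7% to 93.9%, 95.5% or 97.3%, and superiority power from 65.8% to 69.3%, 74.1% or 81.3%. The first set counts as error only if response without the B.4 recoding is the target.

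**The case against.** **B.4 may be a Trial Phase rule.** Its sentence follows one about trialing parameters, and its ending about going on to implant suits a subject not yet implanted. B.4 would then cover the time before implant and B.7.3 the follow-up, and the follow-up and crossover rows above would fall away. This is a serious reading. Against it, B.4 speaks of the whole study, B.6.6 repeats the frequency range without the rule, and B.6.7 defines trial success by pain reduction alone. The Trial Phase row also survives on this reading.

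**The rules may be additive.** B.7.3 does not call its conditions exhaustive, and a 250 Hz ceiling has no direct counterpart in an arm that spans 50 to 1,000 Hz. That stands. The primary endpoint then has a Control-only component that B.7.3, B.8.2 and B.9.2.1 never mention.

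**The sentence on assigned parameters may settle it.** A reader might infer that the plan attaches no consequence at all to other-arm programming, such as a Test subject on Conventional settings. The documents do not support that: this sentence plausibly covers other-arm programming in use at the visit, in both arms. It does not cover brief earlier use. If it barred all earlier use, the two-week conditions would have no purpose.

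**It may hardly ever happen.** Different representatives program the two arms (B.5.2), and crossover opens only after the 6-month assessment (B.6.14). Both make such use before month 3 less likely without excluding it. B.9.2.4 cites a separate SAP for imputation; whether that SAP also fixes responder derivation cannot be checked.

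**Conclusion.** The point holds conditionally. If *failure* in B.4 means primary non-responder, B.4 and B.7.3 give different scores for brief Control use above 250 Hz, in the Trial Phase or early follow-up. B.4 read literally also reaches use after month 3. The effect on the Control count is downward or nil, one Test responder per recoded Control responder at the planning size. Its total size is unknown and may be zero.

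Two stronger conclusions are tempting. One is that the plan flatly contradicts itself on the primary endpoint; B.4 never says what its failure counts towards beyond the programming approach, so this cannot be asserted. The other is that the type I error is inflated to some stated level. Those percentages rest on an assumed frequency and a chosen target, and if use above 250 Hz is itself meant as failure, the result is a one-sided composite definition and not an error. The case for correction rests on the unsettled primary count. It should be fixed, with medium confidence.

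**What to change.** Reconcile B.4 with B.7.3 and B.7.4 before analysis:

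- State what *failure* in B.4 means for the primary endpoint and which period it covers, ending no later than the 3-month assessment for that endpoint.
- Score off-assignment programming, including the other arm's, by one trigger, window and consequence in both arms. If a Control-only component is intended, state it in B.7.3 with the reason.
- Report the number of subjects recoded in each arm.
- Show the primary and 3-month superiority results under the alternative scoring (observed VAS regardless of programming). This is supportive only, because it credits off-assignment stimulation to the assigned arm.

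The cost is wording, a little analysis, and a check that dates and rates of programming changes are captured. Unscheduled visits go on an eCRF (B.6.10), but the device log is optional in Table 1.

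A symmetric rule also has a statistical price. If 5% or 10% of responders in both arms are recoded at 50 per arm, the planning rates become 66.5% vs 47.5%, or 63% vs 45%. Non-inferiority power falls from 92.7% to 90.1% or 87.4%, and superiority power from 65.8% to 60.1% or 54.9%. Error at the margin rises slightly, from 4.7% to 5.4% or 6.3%, because 40% vs 50% shrinks to 38% vs 47.5%, or 36% vs 45%, a gap of less than 10 points. At 67 per arm, about half of the planned 135, non-inferiority power falls from 97.5% to 96.5% or 95.3%.

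All of this concerns scoring only, not which programming a subject should receive.

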Due to the nature of the programs, it is not feasible to blind the subjects, implanting physicians or the clinical site personnel to the DTM-SCS programming and Conventional programming SCS group assignments. Each SCS group will be programmed under the direction of physicians with support of clinical representatives of the Test and Control treatments, which may identify the type of treatment to study participants. Also, open communication about sensation of paresthesia and pain relief is important in adjusting program parameters to provide optimal pain relief for subjects. The assessments of device performance are done by the subjects and not by the site personnel so the lack of blinding of site personnel should not affect results as pain is the major assessment and subjects tend to describe pain truthfully since it affects their everyday life dramatically and not be influenced by knowledge of the device programming. Despite the inability to blind the study, past SCS studies indicate that there is no reason to believe that subjects and Investigators/clinical staff will be influenced one way or another by the knowledge that a particular SCS program has been used. Best efforts will be made to limit bias by training investigators, clinical site personnel, and all clinical representatives on the relevant areas of the study protocol to limit their influence.

B.5.5. Sample Size

Primary Endpoint Assessment occurs at the follow up visit 3 months after Device Activation. Based on the primary endpoint requirement, the estimated sample size of this study is 100 total subjects (approximately 50 subjects in the DTM-SCS group and approximately 50 subjects in Conventional SCS group) who have passed screening requirements, have been randomized, and have completed the primary endpoint assessment. Randomization of approximately 135 subjects is planned to maintain power in the event of attrition.

The clinical investigational plan requires a screening process for all subjects that provide written informed consent. These subjects will undergo screening to assess eligibility. Subjects may be excluded for various reasons during screening. Accordingly, in order to include an estimated 135 subjects to the point of randomization and trial phase, up to 250 subjects may need to be consented and enrolled to account for exclusions prior to randomization.

B.5.5.1 Sample size rationale and statistical power

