The sample size estimate to determine primary endpoint is based on the primary objective of demonstrating non-inferiority of the test group to the control group at 3

months. Established methods were followed in determining the non-inferiority criteria and the related sample size estimate

- Test basis: Farrington-Manning binomial test for non-inferiority
- Estimated responder rate of 70% in the test group and 50% in the control group
- Significance level, alpha, of 0.05 one-sided
- Statistical power = approximately 90% or greater
- Non-inferiority margin of 10%
- Randomization: 1:1

Based on these assumptions, a minimum of 50 randomized and trialed subjects per treatment group (100 total) are required.

B.5.5.2 Overall Sample Size and Enrollment

Based on the primary endpoint requirement, a minimum of 50 subjects per treatment group are required (100 total). To account for a combined estimated attrition of 25% for subjects that do not complete the Trial Phase, and subjects that exit study before the 3-month primary endpoint visit, approximately 135 subjects would need to be randomized and trialed.

To account for 46% attrition prior to randomization (including subject ineligibility after signing the informed consent and subject dropout), it is estimated that a total of up to 250 subjects would need to be enrolled in the study.

B.5.6. Study Duration

This study is expected to last approximately 32 months. Enrollment of subjects is expected to last 18 months. Subjects who are expected to complete the study will commit to it for approximately 14 months. This consists of Baseline assessments, up to 10 days of trial stimulation, and 12 months of treatment following implantation and activation of the device.

B.5.7. Interim Administrative Analyses

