Potential study subjects will be identified from a pool of candidates for SCS therapy that are either affiliated with or referred to the clinical sites. Notice of availability of the study may be used for recruitment purposes, upon approval of the patient recruitment materials by the study IRB(s). An informed consent form (ICF) will be given to the potential subject for private evaluation. The Investigator or Study Clinical Staff will be available to respond to any questions the potential subject may have during evaluation of the ICF. Potential study subjects willing to participate in the study will visit the study site for providing written consent and for evaluation of eligibility based on inclusion and exclusion criteria. Subjects may also be consented via a combination of mail and telephone calls. The RC will document the telephone calls and follow-up by signing the consent once the subject returns the signed consent. The RC will then provide a photo copy to the subject. Once a consented subject is deemed qualified to participate in the study, baseline assessments and randomization will occur followed by scheduling of the trial stimulation phase with the assigned treatment group. Subjects who complete a successful SCS trial phase will be scheduled to receive a permanent implant of leads and the implanted neurostimulator (INS) and will undergo 12 months of stimulation delivery with assessments at 1, 3, 6, 9, and 12 months after the activation of the therapy.

All subjects who remain implanted at or after the 6 month visit, but are not getting sufficient pain relief and would like to try the other treatment arm's parameters will have the option to cross over to the other treatment group (this is an optional two-way crossover). X-ray may be required to determine lead locations. Crossover must be completed within 30 days of the 6 month visit.

Baseline assessments will include measures for pain intensity, use of medication, extent of disability, and quality of life.

Following completion of the baseline assessment, study subjects will be randomized in a 1:1 ratio to either the DTM-SCS programming group or the Conventional SCS programming group.

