After randomization, subjects will undergo a Trial Phase lasting up to 10 days to determine subject's response to assigned treatment group. Temporary or permanent leads and an external neurostimulator (ENS) will be used during the Trial Phase. Subjects will evaluate the assigned treatment group based on pain intensity under optimal parameters. Those who have a "successful Trial Phase" (defined as a 40% or greater pain reduction from Baseline

in their back pain) will proceed to permanent implantation of a SCS system to evaluate the assigned treatment group.

The implanted neurostimulator (INS) will be activated within 14 days after surgical procedure and SCS therapy will be delivered for the next 12 months. Activation of the device marks the initial time point for effectiveness evaluation of the study therapies after implantation. Assessments of pain intensity, use of medication and adverse events will be made at 1 month following Device Activation. At 3, 6, 9, and 12 months after Device Activation, subjects will be assessed for pain intensity, adverse events, extent of disability, use of medication, and quality of life (EuroQol EQ-5D-5L). Patient Global Impression of Change, and subject satisfaction will also be recorded at 3, 6, 9 and 12 months after Device Activation. Subjects have the option to crossover to the other arm after completing the 6 months visit (up to 30 days after completing the 6 month visit).

Figure 1 summarizes the sequence of study-related assessments, procedures, and activities.

[figure not shown]

Figure 1. Study Flowchart

B.6.2. Consent/Enrollment

Medical records of all subjects deemed by the Investigator to be potential candidates for the study will be de-identified and sent to a sponsor designated physician for pre-screening. De-identified medical records should include detailed medical and surgical history of the pain condition under study as well any information about comorbidities. Any imaging studies (such as MRI, CT, X-ray) should be included for evaluation of the study candidate. Once the site has received confirmation that subject may be an appropriate candidate for this study, the site may proceed with the eligibility process. This de-identified pre-screening process assists in reducing unnecessary visits for subjects that would not be eligible for this study.

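### Open allocation is made before the Trial Phase is scheduled, so withdrawals after the arm is known can leave the primary mITT set; randomizing closer to lead placement would cheaply reduce this.

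*Combined protocol and SAP*

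**What the plan says.** The order of events is clear. Section B.6.1 states that, once a subject qualifies, "baseline assessments and randomization will occur followed by scheduling of the trial stimulation phase with the assigned treatment group", and adds: "After randomization, subjects will undergo a Trial Phase lasting up to 10 days". B.6.5 likewise places randomization straight after Baseline. Table 1 gives windows for the end of the Trial Phase, the implant, activation and each follow-up visit, but none for the start of the Trial Phase. B.6.5 and B.6.6 give none either.

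Allocation is open. B.5.4 says "it is not feasible to blind the subjects, implanting physicians or the clinical site personnel" to the assignment, and no step conceals the arm until the procedure.

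B.7.1 defines mITT as "All successfully randomized subjects who complete the Trial Phase" and continues: "The primary analysis of the primary and secondary endpoints will be performed on the mITT population". The other two sets are secondary: "Supportive analyses will be performed for the Intent-to-Treat and Per-Protocol population". The Synopsis describes the endpoint differently: "The primary efficacy endpoint is the percentage of randomized subjects who respond".

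The plan expects some of these losses. B.5.5.2 sets the number randomized "To account for a combined estimated attrition of 25% for subjects that do not complete the Trial Phase" and for exits before the 3-month visit, without a split by arm or stage. Subjects whose Trial Phase is unsuccessful are kept as non-responders (Synopsis, B.7.2), and B.9.2.4 applies multiple imputation to other missing data.

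**The concern.** Between randomization and the trial procedure a subject knows the arm and has not yet committed to lead placement. Someone who withdraws, becomes ineligible or never gets a procedure date in that interval is randomized but cannot enter mITT. Imputing outcomes within mITT does not bring back a subject who is outside it.

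The protocol itself gives a reason why the arm might influence who stays. B.1 says that Conventional SCS has historically not done well for back pain, and reports 3-month responder rates of 80% for DTM-SCS against 51% for Conventional SCS in an ongoing study. B.5.2 relies on randomizing after Baseline to limit selection bias. That protects entry to the study, not retention once the arm is known. At stake is whether the arms compared in the primary non-inferiority test are still the randomized arms.

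**Working it through.** **The plan's own figures.** Inputs from B.5.5.1 and B.5.5.2: responder rates 70% Test and 50% Control, margin 10 points, one-sided alpha 0.05, 50 per arm, attrition 25% after and 46% before randomization.
- Exact power of the Farrington-Manning test at 50 per arm is 92.7%, consistent with the stated target of about 90% or more.
- 100 / (1 − 0.25) = 133.3, against about 135 stated. 135 / (1 − 0.46) = 250, as stated.

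The sample size reproduces and is not at issue.

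**Effect of losses before mITT entry.** The documents give no loss by arm, so the loss fractions and the leavers' response are assumptions. Start from 135 / 2 = 67.5 randomized per arm. Put the true rates among all randomized subjects on the null boundary: Control 50%, Test 40%. If a fraction L of an arm is lost before mITT entry and leavers would have responded at rate q, the rate seen in mITT is

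p_mITT = (p − L·q) / (1 − L), with n = 67.5 × (1 − L), rounded.

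Worked case, 15% of Test and 5% of Control lost, q = 0: Test 0.40 / 0.85 = 0.471 (n = 57); Control 0.50 / 0.95 = 0.526 (n = 64). The mITT difference is −5.6 points instead of −10.

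Reversed, 5% of Test and 15% of Control lost: Test 0.40 / 0.95 = 0.421 (n = 64); Control 0.50 / 0.85 = 0.588 (n = 57). The difference is −16.7 points.

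Probability of declaring non-inferiority, by exact enumeration of the planned test:

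| Lost, Test / Control | Leavers' response | mITT difference | P(non-inferior) |
|---|---|---|---|
| 0% / 0% | none lost | −10.0 | 5.4% |
| 10% / 10% | 0% | −11.1 | 4.6% |
| 10% / 5% | 0% | −8.2 | 7.4% |
| 15% / 5% | 0% | −5.6 | 12.6% |
| 15% / 5% | 20% | −8.0 | 8.0% |
| 20% / 5% | 0% | −2.6 | 20.2% |
| 20% / 5% | 20% | −6.6 | 10.3% |
| 5% / 15% | 0% | −16.7 | 0.9% |
| 15% / 5% | as those who stay | −10.0 | 5.4% |
| 5% / 15% | as those who stay | −10.0 | 5.0% |

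Unequal loss alone does no harm. Equal loss related to outcome moves the result little here. The two together shift the error rate, upwards or downwards according to which arm loses more. Milder assumptions (12% / 4% lost, leavers responding at 30%) leave it at about 5.4%.

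**Would later randomization leave more subjects to analyse?** 25% of 135 is about 34 losses. Assume one third to one half, 11 to 17, occur before the trial procedure. Later randomization moves these ahead of randomization:
- From 250 enrolled, 135 − 11 = 124 to 135 − 17 = 118 would be randomized. Pre-randomization attrition becomes (250 − 124) / 250 = 50.4% to (250 − 118) / 250 = 52.8%.
- Remaining losses are 34 − 11 = 23 to 34 − 17 = 17, leaving 124 − 23 = 101 or 118 − 17 = 101. The present plan leaves 135 − 34 = 101.
- Randomizing 135 would need 250 × 135 / 124 = 272 to 250 × 135 / 118 = 286 enrolled, above the ceiling of 250.

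The number analysable is therefore unchanged at fixed enrolment. If the pre-trial share is near zero, the change has almost no effect on these counts.

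**The case against.** The strongest reply is that the route to bias is the choice of mITT as the primary set, not the date of randomization. The Trial Phase tests the assigned arm, so randomization has to precede it, and a supportive ITT analysis is planned. This largely stands. A reader might infer that randomizing before the Trial Phase is itself an error. The documents do not support that; only the open-ended interval is avoidable.

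Second, no figure shows that these losses occur or differ by arm. B.5.5.2 speaks of about 135 subjects randomized and trialed and gives no pre-trial share. Both arms use the same device system, and crossover is offered after 6 months, which may temper disappointment. This stands as a limit on size: differential loss is a risk, not a documented fact.

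Third, a different company's representatives program each arm (B.5.2), so the arm must be known in order to arrange the procedure. This stands as a cost in notice, not as a barrier, because a date can be fixed before the arm is known.

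Fourth, the affected group is limited. Unsuccessful trials count as non-responders, and subjects lost between Trial Phase completion and month 3 stay in mITT with imputation. That is correct; only losses before Trial Phase completion are in question.

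Finally, Figure 1 is not reproduced in the copy reviewed, so the absence of a limit on the interval is established only for the text and Table 1.

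**Conclusion.** The point holds as a cheap improvement. The order of events, the open allocation and the post-randomization entry condition for mITT are all stated in the protocol, and together they let withdrawals made with knowledge of the arm leave the primary analysis. The size cannot be derived from the documents. In the assumed scenarios the false non-inferiority rate runs from about 1% to 20%, against 5.4% with no loss, and stays near 5% when leavers resemble those who stay.

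Two stronger readings should be resisted. One is that the primary comparison is biased as designed: that needs losses which are both unequal and related to outcome, and nothing in the documents shows either. The other is that later randomization buys power: at 250 enrolled the analysable number is about the same, and the planned power is already met at 50 per arm.

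**What to change.** In B.6.1 and B.6.5, state that a subject is randomized only when eligibility and Baseline are complete and the trial procedure is authorised and dated, within a few days before lead placement. Eligibility and Baseline before randomization are already in the plan; the dated procedure and the short interval are new. Add to the analysis section a table of losses between randomization and Trial Phase completion, by arm and with reasons.

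The cost is protocol wording, a setting in the randomization system, and shorter notice for the arm-specific representative. Pre-trial losses move ahead of randomization, so the 46% pre-randomization attrition in B.5.5.2 should be revised upwards, and 250 enrolled may yield fewer than 135 randomized.

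Subjects who refuse on learning the arm, or who withdraw during the Trial Phase, would still be outside mITT. Making all randomized subjects the primary set, as the Synopsis wording implies, with a stated rule for pre-trial withdrawals, would address that remainder. It complements earlier prevention and does not replace it, because these subjects have no pain score under stimulation and their outcome would have to be imputed or assumed.
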